Production of an immersive VR suite with haptic and user metric feedback would be an advance over current bench top simulator technology, allowing for greater immersion and interaction, leading to better understanding of surgical planning and implementation. The development of this technology could provide trainees with immersive levels of training not previously seen, with improved learning of technical skills over media such as manufacturer technical documents. The effectiveness of training and efficiency of training of the novel immersive VR training systems need to be evaluated as they are increasingly incorporated into competency based, contemporary residency education.

Research Question: Can immersive VR improve the efficiency and competency of technical skill acquisition in senior orthopaedic surgery residents over technical surgical instructional video in learning reverse shoulder arthroplasty?

Research Objective(s):

Primary: To determine if immersive VR is superior to technical surgical instructional video teaching in acquisition of technical skills in learning reverse shoulder arthroplasty

Technical skill outcomes will be determined by Objective Structured Assessment of Technical Skills (OSATS), a Global Ratings Scale (GRS), and competency assessment (pass/fail) by fellowship trained subspecialty shoulder surgeons

Secondary: (1) To determine the efficiency of learning of immersive VR compared to manufacturer specific technical instructional document training of senior residents in learning reverse shoulder arthroplasty.

1. Efficiency will be determined by transfer of training (ToT) and transfer effectiveness ratio (TER)
2. To validate a created VR scoring system with real-world performance (this will include the use of CT scans of cadaveric specimens)

METHODS

Study Design:

A randomized, blinded intervention-control trial directly comparing immersive VR versus technical surgical instructional video training for teaching of reverse shoulder arthroplasty to senior orthopaedic surgery residents will be conducted.

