Residents attending the Canadian Orthopaedic Association (COA), Canadian Shoulder and Elbow Society (CSES) resident training course in Ottawa will be consented for participation. Once consented, residents will be randomized to one of two groups using a computerized blocked protocol based on year of study (R4 and R5) to assure equal level of training between control (technical surgical instructional video) and intervention (immersive VR) groups. Every participant will complete a demographic questionnaire to determine age, handedness, visual correction (eyeglasses), familiarity with shoulder surgery, number of previous courses attended, and familiarity with simulation training and VR. Within the demographic questionnaire will be six questions regarding confidence of performing a reverse shoulder arthroplasty using a modified confidence scale (CS). The demographic questionnaire format will be of Likert-scale responses.

The control group will receive training on completion of a reverse shoulder arthroplasty using a technical surgical instructional video. The control group will be provided as much time as they require to watch the video, including repetition if desired during which they will be timed for completion.

The intervention (VR) group will receive training on completion of a reverse shoulder arthroplasty using an immersive VR simulator (PrecisionOS Technology, Vancouver, BC, Canada). The VR simulator utilizes an HMD producing 3D visuals with haptic controllers for an immersive operating room experience. The module produced consists of the key steps in performing a reverse shoulder arthroplasty using virtual versions of the equipment used in the real procedure. Prior to initiation, participants will be provided with a safety and training demonstration on the use of the VR module by study personnel. The intervention group will similarly be provided as much time as they desire with available repetition as they see fit. The VR group will be timed to task completion as the control group for comparison.

The VR module will provide users with a score based on time to completion of key steps, and performance of key steps such as guide-pin insertion, and overall glenoid baseplate orientation. These positioning scores will be based on clinically relevant cut-off values seen to affect implant longevity. These scores will be subsequently compared to GRS and OSATS scores provided by the assessors for validation purposes.

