Both groups will then be taken to a technical skills laboratory where they will be paired with an assessor (fellowship trained, consultant shoulder surgeon and member of CSES). The assessors will be blinded to the training received by the participant. The participants from both groups will then complete a reverse total shoulder arthroplasty using the same equipment used in either the control (technical surgical instructional video) or intervention (VR) learning activity while being assessed on fresh frozen cadavers (scapula to hand). The assessor will use an OSATS, GRS, and overall competency assessment for the resident during the procedure and for evaluation of the finished product. The assessor will also time the resident for time to task completion, which will be determined by the resident when they explicitly express that they are satisfied with final implantation. Following this, participants will complete a survey assessing their enjoyment of learning activity, perceived benefit to continued use in learning orthopaedic skills, and a re-assessment of their confidence following training modality using the modified confidence scale (CS). The post-cadaveric questionnaire format will be of Likert-scale responses.

As part of the procedure, both the assessor and participant will determine implant parameters once the reverse shoulder arthroplasty is complete. The cadaveric specimens with inserted glenoid baseplates will be CT scanned to provide 2D and 3D reformats. This will allow for determination of the implant orientation parameters including version, inclination, rotation, and offset. These parameters will be compared to the VR scores to determine correlation between the VR training and real-world task completion.

Sampling Design and Subject Selection:

Subjects will be recruited from attendance at the Canadian Shoulder and Elbow Society (CSES) annual meeting by volunteering to participate. Subjects recruited will be in their PGY4 or PGY5 years of orthopaedic residency training and will be from multiple Canadian institutions. Once participants are recruited, study personnel will randomize groups to intervention (VR) or control (technical surgical instructional video) groups via a blocked randomization process in statistical computing software R (R Foundation for Statistical Computing, Vienna, Austria).

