A recent systematic review comparing validity assessments of surgical orthopaedic simulators demonstrates a breadth of cohort variability, with 17.7% to upwards of 50% differences in reported outcome measures between novice/intermediate and expert groupings. TER ratios have seen variations from 7-42% in early VR simulators for novice surgeons. These studies predominantly focus on VR simulators lacking the immersion of contemporary VR, particularly the system from PrecisionOS.

Similarly, the majority of VR simulator research in orthopaedics pertains to arthroscopic surgery which utilizes different global ratings scale outcome measures. The authors of this proposal have recently completed a similar randomized controlled trial at the 2019 CSES meeting (REB approval obtained from the University of Calgary) comparing senior resident VR training to traditional didactic scientific journal training. This resulted in a significant difference in cadaveric task completion time with n=8 in both groups. This study is presently pending publication and in review. As such, for power determination of comparison of VR trained to control group of novice surgeons utilizing a 2-sided test at 5% significance (alpha = 0.05) and to achieve 80% statistical power (beta = 0.02), considering a representative estimated difference of 25% (which we have seen in our previous study, and is conservative regarding similar literature) in combined outcome measures, six subjects will be required for each cohort.

Inclusion Criteria:

1. Individuals registered in licensed post-graduate orthopaedic residency programs attending the CSES resident course and consenting to participation.

Informed Consent:

There will be no direct patient interaction, therapeutic intervention, or other diagnostic or therapeutic intervention related to patient care. Participants will be provided with a consent form outlining the study. Information gathered on participants will not include direct identifiers aside from demographics of age, gender, and training experience. Questionnaires collected will be de-identified using study codes.

The research demonstrates minimal risk to subjects involved as per TCPS2 Chapter 2, and Chapter 10, as the proposed study is observational, does not allow for direct identification of patients, is not staged, and is non-intrusive.

Study Procedures

Randomization: Subjects will be blocked randomized based on year of study (R4 or R5) using computer software.

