Intervention: Study participants will voluntarily complete three questionnaires as well as an activity session utilizing either a technical surgical instructional video or VR to learn reverse shoulder arthroplasty followed by a cadaveric activity in the surgical skills laboratory.

Study Visits: Participants will voluntarily complete study requirements at a single visit during the CSES meeting of which they are electively attending.

Follow-up Visits: No follow-up visits of participating subjects.

Data Collection:

Data collection is prospective following randomization of study participants and blinding of expert raters. Data will be collected in a single setting. Voluntary participants will complete a pre-activity questionnaire identifying age, and gender as well as responses to a number of other questions regarding familiarity with shoulder arthroplasty and surgical simulation/VR as seen in appendix. Post-questionnaire data collected will include questions relating to realism and applicability in learning of the compared modalities and confidence. Questionnaires will be performed during the CSES course on paper/hard copy documents. PrecisionOS, the Lead Researcher, and Co-Researchers will have access to this de-identified data. Hardcopy questionnaires will be retained by the Lead Researcher and kept with PrecisionOS, in a locked and secure office. The hardcopy data will be retained for a period of 10 years. Only designated research personnel will have access to the key to participant de-identified study codes and this will be retained in their locked and secure office. Data will be tabulated to digital format, which will be collected, encrypted and stored on computers owned by the Lead Researcher. This data will then be stored on a secure server. Data will not be transferred out of Canada as per FIPPA. The study will take place once ethics approval is obtained and conclude at the end of the CSES course.

Measures:

Participant specific measures to be collected will include demographics, questionnaire responses, and task completion in an anonymous fashion.

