Primary outcome of comparison of VR to technical surgical instructional video teaching will be assessed by OSATS, GRS, and competency grade provided by evaluators during the sawbone session. Secondary outcomes will be determined using the ToT and TER, overall time difference of task completion between groups, and CER. The cadaveric scapula will be assessed for implant version, inclination, rotation, and offset in the glenoid and recorded for each participant using a CT scan.

Data collection sheet including measures assessed can be seen in appendix.

Analytical Plan

Normality testing will be performed via Shapiro-Wilk test with subsequent mean comparative statistics to determine difference between VR and control groups. Descriptive statistics will be conducted. Likert questionnaire responses will be treated as Likert-scale and Likert-type data using descriptive statistics. Reliability testing for outcome scales in determining internal consistency will be assessed by Cronbach's alpha.

Ethical considerations

Potential Benefits: Study participants will receive expert instructional information regarding shoulder arthroplasty by participating. No remuneration for participation will occur. Longitudinal benefits could include improved technical skills in reverse shoulder arthroplasty.

Potential Risks: No direct risks to study participants involved. Subject recruitment is free of coercion, and only de-identified demographic data used with adherence to FIPPA and TCPS2 guidelines for data handling and storage.

Subject Safety Provisions: No direct risks to study participants. Occasionally use of immersive VR can produce feelings of nausea. This will be dictated to study participants prior to commencing the study, and participants are free to withdraw at any time. Safety provisions include data handling and transfer of patient information with adherence to FIPPA and TCPS2 guidelines and all attempts to store and utilize de-identified data.

Ethics Approval: Fraser Health Research Ethics Board (REB); Calgary REB

Plans for Publication and conference presentations:

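### Do the sawbone session, the document comparator and the open inclusion criterion leave the trial's outcome, control arm or population undefined?

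*Combined protocol and SAP*

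**What the plan says.** Three lines in the combined protocol and SAP are at issue.

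- **Assessment setting.** Measures defines the primary outcome by OSATS, GRS and a "competency grade provided by evaluators during the sawbone session". Study Design has participants perform the arthroplasty "while being assessed on fresh frozen cadavers (scapula to hand"), and Study Procedures describes training "followed by a cadaveric activity in the surgical skills laboratory".
- **Comparator.** The secondary objective concerns the "efficiency of learning of immersive VR compared to manufacturer specific technical instructional document training of senior residents". Study Design says: "The control group will receive training on completion of a reverse shoulder arthroplasty using a technical surgical instructional video".
- **Population.** The only entry under Inclusion Criteria is: "Individuals registered in licensed post-graduate orthopaedic residency programs attending the CSES resident course and consenting to participation". Sampling Design and Subject Selection says: "Subjects recruited will be in their PGY4 or PGY5 years of orthopaedic residency training". Randomisation is blocked by year of study, with R4 and R5 the only years named.

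**The concern.** A protocol should fix its primary outcome, its comparator and its population without leaving the reader to infer them. Here one sentence on each disagrees with, or is looser than, the design.

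A sawbone is a different test object from a cadaver. Taken literally, the primary ratings would come from a session that is not otherwise described. The validation objective would then compare VR scores with ratings made on one object and with CT measurements made on another.

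The efficiency objective would name a training medium that no participant receives. Reading a document and watching a video may take different times, so the control side of the transfer of training and transfer effectiveness ratio would be unclear.

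A junior resident who met the listed criterion would have no randomisation stratum. With six per arm, a single such resident would be a visible share of the data.

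**Working it through.** The plan gives no figure for these points, so the check is to set the relevant sections side by side and ask whether more than one reading can be carried out.

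**1. Where are the primary ratings made?**

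- Study Design: blinded assessors score OSATS, GRS and overall competency during the procedure on cadavers and on the finished product.
- Study Procedures: one training activity, then one cadaveric activity, at a single visit.
- Data Collection: data are gathered in a single setting.
- Measures: two sentences after the word sawbone, the cadaveric scapula is to be CT scanned for implant position.

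The instruments in Measures are the same three that Study Design assigns to the cadaver procedure. No other rated session is described. The only executable reading is that the ratings are made on the cadaver, so ratings and CT parameters come from the same specimen.

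**2. What is the control training?**

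- Video: the research question, the primary objective, the opening of Study Design, its randomisation, control-group and assessment paragraphs, Sampling Design and Subject Selection, Study Procedures, and the primary-outcome sentence in Measures.
- Document: the secondary objective. The Purpose section also mentions manufacturer documents, but only as a general comparison of media.

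Study Design states that control participants are timed while they watch the video, repeats included. The protocol gives no formula for the two efficiency measures. Whatever formula is used, the only control training time recorded is video time. The secondary-outcome sentence in Measures compares the groups without naming a document.

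**3. Who can be enrolled?**

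- Inclusion Criteria: registered orthopaedic residents at the course who consent, with no year stated.
- Sampling Design and Subject Selection: PGY4 or PGY5.
- Randomisation text in Study Design and Study Procedures: R4 and R5 only.
- Research question and opening of Study Design: senior residents.

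The broad entry and the narrower selection rule can both be applied. Together they admit registered, consenting PGY4 and PGY5 residents at the course, which is the population the two strata cover.

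**4. How much could it matter?**

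The planned size is six per cohort. One resident outside the strata would be 1/6 = 0.167, about 17% of an arm. That assumes enrolment against the selection rule. The documents do not say that junior residents attend the course, and they give no variance by year from which an effect on precision could be computed.

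**The case for a change.** The strongest case for acting is that all three discrepancies stand in the current text and would cost only a few words to correct. The sawbone wording sits in the sentence that defines the primary outcome, where an ethics board or a later reader checking reported outcomes would look first. The background describes the group's previous trial, in which controls read a journal article, so the word document could mislead someone about the present comparator. On eligibility, the opening of Study Design also speaks simply of residents attending the course. The power paragraph calls participants novice surgeons where the rest of the protocol calls them senior, so the listed criterion is not the only loose statement of population.

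The textual part of this stands: two wordings are wrong, and the criterion list is less complete than the selection section. The consequences do not follow. No second session exists in which ratings could be made. No document is assigned to anyone. The selection section excludes the junior resident on whom the stratification argument depends. Even the case for correction accepts that the intended meaning can be recovered from the other sections and that no procedure, sample size or analysis would change.

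**Conclusion.** No change to the plan follows. The sawbone and document wordings are clerical slips that the surrounding text resolves in one direction only. The missing year in the inclusion criterion is supplied by Sampling Design and Subject Selection and by the randomisation strata. The effect on allocation, outcome data, efficiency inputs and sample size is nil, because any correction would restate what the protocol already specifies. The 17% figure is arithmetic on a participant the protocol does not admit, so it does not measure a risk in this trial.

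This rests on two assumptions: that the protocol is read as a whole, and that the appendix data sheets, which were not available here, do not introduce a separate sawbone session. If the protocol is reissued for another reason, the wording can be tidied then. Doing so would improve consistency without altering the trial.

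### Residents are block-randomised by year of training (R4/R5), but the Analytical Plan names no between-group test and no term for year

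*Combined protocol and SAP*

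**What the plan says.** **Randomisation.** Study Design describes a "computerized blocked protocol based on year of study (R4 and R5) to assure equal level of training" in the two groups. Study Procedures, under Randomization, repeats it: "Subjects will be blocked randomized based on year of study (R4 or R5) using computer software". Sampling Design and Subject Selection says allocation is made "via a blocked randomization process in statistical computing software R". No block size is given. The same section fixes the two levels of the factor: "Subjects recruited will be in their PGY4 or PGY5 years of orthopaedic residency training".

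**Sample size.** At two-sided 5% significance and 80% power, "considering a representative estimated difference of 25" per cent in combined outcome measures, the plan concludes that "six subjects will be required for each cohort". No SD is given.

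**Analysis.** The Analytical Plan's only statement on the group comparison is "Normality testing will be performed via Shapiro-Wilk test with subsequent mean comparative statistics to determine difference between VR and control groups". The rest covers descriptive statistics, handling of Likert responses and Cronbach's alpha. No group-comparison test, model, stratum or covariate is named, and nothing is said about what follows if normality fails. The appendix is cited for the questionnaire items and the data collection sheet, not for analysis.

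**The concern.** Year was used in the randomisation because level of training might affect performance. If it does, balancing year across the arms makes the difference in means more precise than a plain two-group test recognises. The between-year spread stays in the residual variance, the standard error is too large, and the test rejects too rarely. A comparison that includes year removes that spread.

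With a stated requirement of 12 residents there is little precision to spare. Leaving both the test and the use of year open also allows them to be chosen after the scores are seen.

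**Working it through.** **1. The plan's own figure.** Six per arm cannot be reproduced, because no SD is stated. It can only be solved backwards. A two-sample t-test with 10 df, two-sided 5%, has 80% power at six per arm when the noncentrality d × √(6/2) is 3.110, so d = 3.110/1.732 = 1.80 SD (1.7955 before rounding). If the 25% means 25 points on a 0–100 scale (an assumption), the implied SD is 25/1.7955 = 13.9 points.

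**2. Assumed inputs.** Normal scores; 3 R4 and 3 R5 in each arm; an R4/R5 gap g of 0, 0.5 or 1 within-year SD. The documents give no value for g.

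**3. Formulas.**
- Unadjusted t-test, 10 df: the difference in means is unaffected by g. The residual sum of squares, in units of the within-year variance, is noncentral chi-square with 10 df and noncentrality 12 × 0.25 × g² = 3g². At g = 1 that is 3. Power follows by integrating over this distribution, with critical value 2.228.
- Linear model with arm and year, 9 df: noncentral t with noncentrality d√3 and critical value 2.262, whatever the gap.

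**4. Which SD was used in planning.** With balanced years, the total SD is √(1 + g²/4) within-year SDs: 1.031 at g = 0.5 and 1.118 at g = 1. If the planning SD includes year, the 1.7955 SD effect becomes 1.7955 × 1.031 = 1.851 or 1.7955 × 1.118 = 2.007 within-year SD.

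| Gap (within-year SD) | Unadjusted size | Planning SD includes year: power unadjusted v adjusted | Planning SD is within-year: power unadjusted v adjusted |
|---|---|---|---|
| 0 | 5.0% | 80.0% v 79.0% | 80.0% v 79.0% |
| 0.5 | 4.3% | 80.2% v 81.4% | 77.8% v 79.0% |
| 1 | 2.8% | 80.9% v 87.1% | 71.0% v 79.0% |

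The adjusted test has size 5% throughout. The two powers cross at a gap of about one third of an SD (0.33 on the within-year scale, 0.34 on the total scale). Below that, adjusting loses up to 1 point.

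**5. If incomplete blocks leave years unequal.** The cost of adjusting when year has no effect rises with the variance inflation. At R4:R5 of 4:2 in one arm and 3:3 in the other, inflation is 1.029 and adjusted power 77.9%, about 2 points below 80%. At 4:2 v 2:4 it is 1.125 and 74.2%, about 6 points below.

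**6. Permutation alternative.** With balanced years there are 20 × 20 = 400 allocations stratified by year. Simulated size is about 5% and power 78.4% at 1.80 within-year SD, close to the linear model's 79.0%.

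**The case against.** **The size of the problem is not in the documents.** This stands. The gap, the SD and the standardised effect are all assumed, and nothing supports a full SD between adjacent years. Six per arm is also a minimum. At eight per arm, the size of the previous trial, an effect of 1.80 within-year SD gives 90% v 91% at a 0.5 SD gap and 86% v 91% at 1 SD.

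**A reader might infer that ignoring year takes the trial from its planned 80% power to 71%.** The documents do not support that as the main reading. The 25% difference is attributed to the team's previous trial, which the background says enrolled both PGY4 and PGY5 residents. An SD from that trial would already contain any year effect. On that scale the unadjusted test keeps its 80%, and adjustment is a gain, not a repair.

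**A reader might infer bias or extra false positives.** With years balanced there is neither; the error is towards missing a real difference. Unequal arms would shift the unadjusted difference by part of the year gap. But the stated aim is equal training level, and residents are randomised once recruited, which is compatible with allocating from a known list. With six R4 and six R5, a 4:2 v 2:4 split cannot arise with blocks of 2 or 6. With blocks of 4 its probability is 2 × 1/6 × 1/6 = 1/18.

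**The wording does not forbid adjustment.** True. The point is that none is planned.

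**Pass/fail.** The primary objective also lists a "competency assessment (pass/fail) by fellowship trained subspecialty shoulder surgeons". A reader might infer that this grade will be compared by means. The Analytical Plan does not say so for that grade, and its method is a separate question.

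**Conclusion.** The point holds as a minor one. The design uses year and the analysis plan does not; nor does it name the test that will compare the arms. If the comparison is run as a plain two-group test with balanced years, it is valid but conservative whenever R4 and R5 differ.

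At six per arm, including year changes power by about −1, +1 and +6 points at gaps of 0, 0.5 and 1 SD if the planning SD includes year, and by about −1, +1 and +8 points if it is within-year. These figures rest on normal scores, three residents of each year per arm, and an effect back-solved from the stated power. The gain may be small, or slightly negative if the gap is under about one third of an SD. The case for the change is that it follows the randomisation, uses data already held and settles the test in advance.

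**What to change.** In the Analytical Plan, name one between-group analysis for OSATS and GRS before any scores are seen. Either of these would serve:
- a linear model with arm and year (R4/R5), without an interaction; or
- a permutation test of the arm difference, stratified by year.

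The choice should be fixed in advance, not made by the Shapiro-Wilk result. With 12 residents that check has little power: in simulation it rejects residuals from exponential data only about 21% of the time. It can stay as a descriptive check.

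The cost is a line or two of text, no new data and, for the linear model, one degree of freedom. If year has no effect, adjustment loses about 1 point of power with balanced years and somewhat more if incomplete blocks leave them unequal. Stating the block size would show how likely that is.

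### The pass/fail competency grade is a primary measure, but the Analytical Plan names no test suited to it; its one rule, a normality test then a comparison of means, does not fit binary data

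*Combined protocol and SAP*

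**What the plan says.** The primary objective, under Research Objective(s), lists three technical-skill outcomes. The third is a "competency assessment (pass/fail) by fellowship trained subspecialty shoulder surgeons", so it is binary. The Measures section repeats the set: the primary comparison "will be assessed by OSATS, GRS, and competency grade provided by evaluators". Neither place ranks the three.

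The Analytical Plan has one sentence on comparing the arms: "Normality testing will be performed via Shapiro-Wilk test with subsequent mean comparative statistics to determine difference between VR and control groups". The rest of that section covers descriptive statistics, Likert responses and Cronbach's alpha. It names no test for proportions, no exact test and no particular means test, and it does not say what follows if normality is rejected.

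The power paragraph under Sampling Design and Subject Selection plans on "utilizing a 2-sided test at 5% significance (alpha = 0.05") and concludes that "six subjects will be required for each cohort".

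**The concern.** A primary measure needs an analysis fixed before the data are seen. Two readings of the plan are open. If the sentence covers pass/fail, the normality step is empty and the means comparison relies on a t distribution that six 0/1 values per arm do not follow. If it does not, a primary measure has no planned test. The same edit is needed either way.

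What is at stake is a borderline competency result. With 12 residents there are few possible tables. For a plausible one, two ordinary ways of comparing means fall on opposite sides of 5%, so the choice could be made after the result is known.

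**Working it through.** **Inputs.** From the documents: two-sided 5% test, six per arm, binary competency grade. No expected pass rate is given, so a range of common true pass rates p is assumed, with q = 1 − p.

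**The plan's own figure.** Six per arm cannot be reproduced, because no standard deviation is given. With n = 2(1.96 + 0.84)²·SD²/0.25², an SD of 0.15 gives 5.6, rounded up to 6, so six follows only for an SD near 0.15. Read as pass rates of 50% v 75%, the same inputs need 58 per arm. The sample size was therefore not built on pass/fail.

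**Step 1: Shapiro-Wilk on six binary values.**

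| Passes in arm | p |
|---|---|
| 1 or 5 | 0.00002 |
| 2 or 4 | 0.00135 |
| 3 | 0.00404 |
| 0 or 6 | no variance, uninformative |

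**Step 2: one table worked through, 6/6 v 3/6.**

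- Means are 1 and 0.5. Sample variances are 0 and 6 × 0.25/5 = 0.3.
- Equal-variance t: pooled variance 0.15, SE = √(0.15 × 2/6) = 0.224, t = 0.5/0.224 = 2.24 on 10 df, p = 0.049.
- Welch: same t, but df = (0.3/6)² / [(0.3/6)²/5] = 5, p = 0.076.
- Fisher: one tail is C(6,3)/C(12,9) = 20/220 = 0.091, so two-sided p = 0.18.
- Boschloo: the probability of a table with a Fisher p no larger than this one, maximised over p, is 0.068.

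**Step 3: the tables near the boundary at 6 v 6.** Each row also covers the mirror images.

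| Passes | Equal-variance t | Welch | Boschloo | Fisher |
|---|---|---|---|---|
| 6 v 3, 3 v 0 | 0.049 | 0.076 | 0.068 | 0.18 |
| 6 v 2, 4 v 0 | 0.010 | 0.025 | 0.021 | 0.061 |
| 5 v 1 | 0.018 | 0.018 | 0.039 | 0.080 |
| 6 v 1, 5 v 0 | 0.0005 | 0.004 | 0.006 | 0.015 |

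Of the 49 possible tables, the equal-variance t rejects 16, Welch and Boschloo the same 12, and Fisher 6.

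**Step 4: true type I error at 6 v 6.** This is the sum of C(6,a)·C(6,b)·p^(a+b)·q^(12−a−b) over the rejected tables (a, b). At p = 0.5 each table has weight C(6,a)·C(6,b)/4096:

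- 6 v 0: 2 × 1 = 2
- 6 v 1 and 5 v 0: 4 × 6 = 24
- 5 v 1: 2 × 36 = 72
- 6 v 2 and 4 v 0: 4 × 15 = 60
- 6 v 3 and 3 v 0: 4 × 20 = 80

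Equal-variance t: 238/4096 = 5.8%. Welch and Boschloo (without the last line): 158/4096 = 3.9%. Fisher (first two lines): 26/4096 = 0.6%.

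At p = 0.7 Welch and Boschloo have 2.4%. The four extra t-test tables add 40(p³q⁹ + p⁹q³) = 40 × 0.001096 = 4.4 points, giving 6.8%.

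| Common pass rate | Equal-variance t | Welch and Boschloo |
|---|---|---|
| 50% | 5.8% | 3.9% |
| 70% (or 30%) | 6.8% | 2.4% |
| 75% | 6.4% | 1.7% |
| 80% | 5.3% | 1.0% |
| 85% | 3.6% | below 1% |
| 90% | 1.7% | below 1% |

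The maximum for the equal-variance t is 6.8%, near p = 0.69.

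**Step 5: other arm sizes.** Repeating the enumeration at p = 0.5, Welch has a true type I error of about 6.2% at 7 v 6 and 7.7% at 8 v 8. These sizes are feasible: participants are course volunteers, and the sponsor's earlier trial had eight per arm.

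**The case against.** The strongest reply is that the plan never says a t-test will be applied to pass/fail. A sentence that opens with normality testing reads naturally as being about scores and times, and the pass/fail grade might simply be described. That stands. A reader might infer that the sponsor has chosen an invalid test for competency, but the documents show only an unrestricted rule and no stated alternative.

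A second reply is that Welch is also a comparison of means, and at 6 v 6 it makes the same 5% decisions as Boschloo. Asymptotic Mann-Whitney has the same error rate there. That also stands, so it would be wrong to say that the stated rule in general inflates type I error at the planned size. It does not rescue the rule, because the plan does not name Welch and Welch exceeds 5% at other feasible sizes.

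Third, the Fisher figure of 0.18 makes the contrast look larger than it is. Fisher's true size here is at most 0.6%, and for 6/6 v 2/6 and 5/6 v 1/6 Boschloo agrees with the t-test. Only 6 v 3, 3 v 0 and their mirrors are significant by the equal-variance t but by neither Boschloo nor Fisher.

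Finally, pass/fail has little power at this size whatever the test. At an assumed 50% v 75%, Boschloo has about 11% and Fisher about 2.5%. That lowers the practical stakes, but it is no reason to leave a primary measure without a suitable method.

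**Conclusion.** The point holds as a gap in specification with a modest numerical consequence. The only stated between-arm rule does not suit a binary primary measure, its normality step is meaningless there, and the unnamed means test can decide a borderline result (0.049 or 0.076 for 6/6 v 3/6). At 6 v 6 the excess type I error belongs to the equal-variance t-test alone. It peaks at 6.8% and disappears at pass rates of 85% or more. Welch is safe at 6 v 6 but not at every size the trial might reach.

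The figures assume independent residents and a common true pass rate under the null, and the documents give no expected rate. It would also go too far to treat competency as the leading measure, since the three are not ranked. This is something the sponsor should fix; the size of the error does not make it critical.

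**What to change.** In the Analytical Plan:

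- Limit the normality test and the comparison of means to OSATS, GRS and the time outcomes.
- State that pass/fail will be compared by one named two-sided exact test, for example Boschloo's, with no normality test. Report the difference in pass proportions with an exact 95% confidence interval, and name the interval method.

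The plan should not list which tables will count as significant, because the final arm sizes may differ from six and the boundary moves with them.

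The cost is about two sentences and standard software, with no extra participants or data. The downside is that some borderline tables, such as 6/6 v 3/6, lose the nominal significance that an equal-variance t-test would give them. The change should be made before results by arm are seen.
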